Estimators	Main estimator: Imputed datasets will be analyzed using quantile regression models used for primary analysis to obtain estimates and standard errors (standard errors obtained through bootstrap methods). Results of the estimates and standard errors will be combined using Rubin's rule to estimate the median difference (filgotinib - placebo) in change or percentage change from baseline, 95% CI for the sperm/semen parameter of interest.

6.5. Other Displays of Sperm/Semen Data

6.5.1. Week 26 by Treatment Sequence and Responder/Non-Responder at Week 13 Displays

Displays will be presented at the Week 26 visit for the following 4 groups:

- filgotinib responder at Week 13 switched to open-label filgotinib
- filgotinib non-responder at Week 13 switched to standard of care
- placebo responder at Week 13 switched to standard of care
- placebo non-responder at Week 13 switched to standard of care

The number and proportion of subjects with a $\geq 50\%$ decrease from baseline in sperm concentration at the Week 26 visit will be presented. An exact 95% CI for the proportion of subjects with a $\geq 50\%$ decrease from baseline in sperm concentration at Week 26 within treatment sequence and responder/non-responder status group will be presented based on the Clopper-Pearson method.

For all secondary continuous endpoints, 8-point summary statistics (n, mean, SD, median, Q1, Q3, minimum, and maximum) by treatment sequence and responder/non-responder status at Week 13 will be provided for the value at the visit, change from baseline, and percentage change from baseline in sperm/semen parameters at Week 26. A 95% distribution-free CI on the median change and percentage change from baseline at Week 26 in all sperm/semen parameters will be constructed by treatment sequence and responder/non-responder status at Week 13 using the CIPCTLDF option in PROC UNIVARIATE in SAS.

A cumulative distribution plot for percentage change from baseline in sperm concentration at Week 26 will be constructed by treatment sequence and responder/non-responder status at Week 13 for those who remain on study drug at the Week 26 visit.

6.5.2. Treatment Sequence Displays at/after Week 39

Displays will be presented by analysis visit at Week 39 and thereafter in the Extension Phase for the following 3 treatment sequences:

- filgotinib to open-label filgotinib
- filgotinib to standard of care
- placebo to standard of care

The number and proportion of subjects with a $\geq 50\%$ decrease from baseline in sperm concentration will be presented by analysis visit.

For all secondary continuous endpoints, 8-point summary statistics (n, mean, SD, median, Q1, Q3, minimum, and maximum) by treatment sequence will be provided for the value at the visit, change from baseline, and percentage change from baseline in sperm/semen parameters.

6.5.3. Pre-Specified Sperm Decrease Threshold Criteria and Confirmed Semen Abnormalities

Subjects who met a pre-specified sperm decrease threshold (a $\geq 50\%$ decrease from baseline in sperm concentration and/or motility and/or morphology) were to stop study drug and begin a standard of care regimen selected by the investigator in accordance with the protocol and be followed off study drug to evaluate for reversibility criteria.

A “confirmed semen abnormality” as defined by Jarvi and colleagues {[Jarvi 2008](#)} reflects the presence of abnormal sperm parameters potentially associated with decreased male fertility; the criterion is met when one or more of the following are observed: a sperm concentration $< 5 \text{ M/mL}$, or sperm motility $< 20\%$, or a percent normal sperm morphology of $< 10\%$.

The number and proportion of subjects meeting any of the sperm decrease thresholds (from the baseline value [mean of 2 evaluable semen collections at screening]) or any of the components of a confirmed semen abnormality (mean of 2 evaluable samples at a study visit) at Week 13 will be displayed by double-blind treatment group for the Semen Analysis Set.

Sperm Decrease Criteria

- $\geq 50\%$ decrease in sperm concentration
- $\geq 50\%$ decrease in sperm total motility
- $\geq 50\%$ decrease in sperm morphology [% normal] (WHO 1992 criteria)
- $\geq 50\%$ decrease in sperm concentration and ($\geq 50\%$ decrease in total motility and/or morphology [% normal]) at the same visit)

Confirmed Semen Abnormality Criteria (as defined by Jarvi et al)

- Sperm concentration $< 5 \text{ M/mL}$
- Sperm total motility $< 20\%$
- Sperm morphology (% normal) $< 10\%$
- Confirmed Semen Abnormality (Sperm concentration $< 5 \text{ M/mL}$ or sperm total motility $< 20\%$ or sperm morphology [% normal] $< 10\%$ at the same visit)

The number and proportion of subjects meeting any of the pre-specified sperm decrease thresholds or components of a confirmed semen abnormality will be displayed at Week 26 for the Week 26 Semen Analysis Set; and at or after the Week 39 visit for the At/After Week 39 Semen Analysis Set. Presentations will be displayed by treatment sequence and responder/non-responder at Week 13 and treatment sequence, respectively.

A listing of subjects who met any of the components of a confirmed semen abnormality will be provided.

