### 3.2. Extension Phase

**Figure 3-3. Extension Phase – Evaluation**

\*Open-label treatment with filgotinib or Standard of Care. Adjustment of background treatment with non-prohibited medication allowed at any time during the Extension Phase

In the Extension Phase, subjects will receive open-label treatment (filgotinib or Standard of Care) and have a study visit every 13 weeks that includes semen analysis. The first scheduled visit of the Extension Phase occurs at Week 26.

In case sperm parameters at any visit (including Week 156) meet any of the pre-specified decrease thresholds, subjects will enter the Monitoring Phase.

During the Extension phase, Standard of Care and background treatment concomitant to filgotinib may be optimized at the discretion of the investigator, taking into consideration the protocol restrictions.

[figure not shown]
In case a subject needs to be treated with a prohibited medication (see [Table 5-1](#)), for instance to control their rheumatic condition, the subject will discontinue the study and complete an Early Termination (ET) visit (including semen collection). For subjects on filgotinib, this will be followed by a safety follow-up visit 30 days after last study drug dose.

All subjects who did not enter the Monitoring Phase will continue the study until the Week 156 visit.

In the Extension Phase, subjects must have yearly Quantiferon® testing. Yearly TB testing begins 1 year from the screening TB test date. If yearly TB testing falls between study visits, the yearly TB testing should be performed at the visit prior to 1 year from the screening TB test date. Subjects with newly positive (converted) Quantiferon® (or centrally reported equivalent assay) TB test should be discontinued from the study. Subjects who were previously treated for TB with a complete and adequate course of therapy as per local Standard of Care and as verified by the investigator do not need to have yearly tests.

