**Table 5-1. Prohibited Concomitant Medications**

Drug Class	Agents Disallowed	Prohibited Period
Strong P-gp Inducersa		
Anticonvulsants	Including, but not limited to Phenobarbital, phenytoin, carbamazepine	21 days prior to Screening through the end of the Double-blind Treatment Phase of the study and through the end of the Extension Phase for subjects on open-label filgotinib
Antimycobacterials	Including, but not limited to Rifabutin, rifapentine, rifampin	
Herbal/Natural Supplements	St. John's wort and danshen ( Salvia Miltiorrhiza )	
Prohibited Medications for Rheumatic Conditions		
Corticosteroids	Dose equivalent to >10 mg/day of prednisone or equivalent (oral) For subjects on Standard of Care treatment: dose equivalent to >20 mg/day of prednisone or equivalent (oral) All parenteral corticosteroids are prohibited During the Extension and Monitoring Phase, subjects may receive a maximum of 3 intra-articular injections of corticosteroid every 12 months; The dose of corticosteroid injected should not exceed the equivalent dose of triamcinolone 40-mg suspension; The dose and volume should be adjusted downward as appropriate to the size of the joint	Randomization through the end of the study
TNF $\alpha$ antagonist	Including, but not limited to: infliximab, adalimumab, etanercept, golimumab, certolizumab, and biosimilar agents	4 weeks prior to Screening through the end of the Double-Blind Treatment Phase of the study and through the end of the Extension Phase for subjects on open-label filgotinib
Interleukin antagonists	Including, but not limited to: ustekinumab, toccilizumab, secukinumab, anakinra,	12 weeks prior to Screening through the end of the Double-Blind Treatment Phase of the study and through the end of the Extension Phase for subjects on open-label filgotinib
JAK inhibitor	Any JAK inhibitor other than filgotinib	90 days prior to Screening through the end of the Double-Blind Treatment Phase of the study and through the end of the Extension Phase for subjects on open-label filgotinib

Drug Class	Agents Disallowed	Prohibited Period
	Filgotinib	Any time prior to Randomization in this study

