3.2. Subject Grouping

For analyses based on the All Randomized and ITT Semen Analysis Sets, subjects will be grouped according to their randomized treatment. For all other analysis sets, subjects will be grouped according to the actual treatment received. The actual treatment received will differ from the randomized treatment only when the actual treatment differs from randomized treatment for the entire treatment duration of the study drug administration period.

The following subject groupings will be applied to the semen and hormone data according to the actual treatment received:

- For the double-blind treatment phase, data will be summarized by double-blind treatment group (ie, filgotinib 200 mg and placebo).
- For the Week 26 visit, semen and hormone data will be summarized by treatment sequence and Rheumatic Disease Responder/Non-responder status at Week 13 (ie, filgotinib responders who switch to open-label filgotinib, filgotinib non-responders at Week 13 who switch to standard of care, placebo responders who switch to standard of care, and placebo non-responders who switch to standard of care).
- Semen and hormone data collected at/after Week 39 in the extension phase will be summarized by treatment sequence (ie, double-blind filgotinib to open-label filgotinib, double-blind filgotinib to standard of care, and placebo to standard of care) for subjects with baseline and ≥ 1 visit at/after Week 39.

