3.7. Analysis Visit Windows

3.7.1. Definition of Study Day

The First Dosing Date of Double-Blind Filgotinib/Placebo is defined as the date when subjects take their first dose of double-blind filgotinib/placebo as recorded on the Study Drug Administration eCRF.

The Last Dosing Date of Double-Blind Filgotinib/Placebo is defined as the date when subjects take their last dose of double-blind filgotinib/placebo as recorded in the Study Drug Administration eCRF.

The Last Dosing Date of Any Filgotinib is defined as the date when a subject takes their last dose of double-blind or open-label filgotinib as recorded in the Study Drug Administration eCRF.

The Start Date of Extension Phase is defined as the first dose date of open-label filgotinib (for rheumatic disease responders randomized to filgotinib who continued on open-label filgotinib in extension phase) from the study drug administration eCRF or last dose date of double-blind study drug +1 day for subjects who have a non-missing standard of care start date in the extension phase of the study. In some countries, it takes time to obtain a new standard of care drug for rheumatic disease when subjects undergo a medication switch (especially for biologics), so the “standard of care” is to continue background medications alone or in rare cases, to take no rheumatic disease medication until the new regimen is available.

The End Date of Extension Phase is defined as last dose date of open-label filgotinib as recorded on the Study Drug Administration eCRF for subjects on open-label filgotinib in the Extension Phase. The end date for standard of care in extension phase will be 1 day prior to the date the subject went into the Monitoring Phase (ie, date the site was notified of subject meeting a prespecified sperm decrease threshold). Subjects who do not participate in Monitoring Phase but have a Study Completion eCRF that states that the subject has either completed study or prematurely discontinued study will have the last date of standard of care estimated using the last of the following dates: last Covance lab date, last eCRF visit date, date of last sperm sample collection, and death date (if subject died).

Study Day will be calculated from the first dosing date of double-blind filgotinib/placebo and derived as follows:

- For postdose study days: Assessment Date – On-Filgotinib/Placebo Study Day 1 + 1
- For days prior to the first dose: Assessment Date – On-Filgotinib/Placebo Study Day 1

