6.6.3. Hormones

Similar analysis methods used to summarize continuous secondary semen parameters will be used to analyze hormones LH, FSH, inhibin B, and total testosterone. Baseline will be the last value prior to administration of any study drug.

For all continuous hormone parameters, 8-point summary statistics (n, mean, SD, median, Q1, Q3, minimum, and maximum) by treatment (double-blind treatment group for Baseline, Week 4 and Week 13; by treatment sequence and responder/non-responder status at Week 13 for Baseline and Week 26) will be provided for the value at the visit, change from baseline, and percentage change from baseline in hormone parameters for the Semen Analysis Set and Week 26 Semen Analysis Set, respectively. A 95% distribution-free CI on the median change and percentage change from baseline in all hormone parameters will be constructed by double-blind treatment group at Weeks 4 and 13; and by double-blind treatment and responder/non-responder status at Week 13 for the Week 26 visit using the CIPCTLDF option in PROC UNIVARIATE in SAS.

Quantile regression will be used to estimate the difference (filgotinib minus placebo) in median change and percentage change from baseline in hormones at double-blind Weeks 4 and 13 and to construct a 95% CI. Models will adjust for the baseline hormone value, concurrent MTX use (yes, no), and sperm concentration strata (15 - 50 M/mL, > 50 M/mL). The CI=RANK option will be specified in PROC QUANTREG in SAS.

For Week 26, the change and percentage change from baseline in hormone parameters will be displayed by treatment sequence, responder/non-responder status at Week 13, and visit for subjects in the Week 26 Semen Analysis Set.

For visits at/after Week 39, the change and percentage change from baseline in hormone parameters will be displayed by treatment sequence and visit for subjects in the At/After Week 39 Semen Analysis Set.

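### SAP 6.5.3: the proportion at or after Week 39 appears to pool men with 1 to 10 semen visits, so for most criteria it depends on visits contributed as well as on risk per visit

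*SAP*

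**What the plan says.** - SAP 6.5.3 covers the four decrease criteria (concentration, motility, morphology, and concentration combined with either of the others) and the confirmed-abnormality criteria, at Week 26 "and at or after the Week 39 visit for the At/After Week 39 Semen Analysis Set". Its grouping sentence reads "Presentations will be displayed by treatment sequence and responder/non-responder at Week 13 and treatment sequence, respectively". The period from Week 39 is therefore split by sequence only.
- Other sections treat the same period by visit. SAP 6.5.2 states "Displays will be presented by analysis visit at Week 39 and thereafter in the Extension Phase for the following 3 treatment sequences", but the only proportion it lists is the 50% concentration decrease; the other semen parameters get continuous summaries. SAP 6.6.3 says that hormone changes "will be displayed by treatment sequence and visit for subjects in the At/After Week 39 Semen Analysis Set".
- SAP 3.2 says "Semen and hormone data collected at/after Week 39 in the extension phase will be summarized by treatment sequence", for men with a baseline and at least one visit in that period. Semen is collected every 13 weeks to Week 156.
- Follow-up rules differ by sequence. In Protocol Table 5-1, TNF antagonists, interleukin antagonists, other JAK inhibitors and several other DMARDs stay prohibited after Week 13 only "through the end of the Extension Phase for subjects on open-label filgotinib". Under Protocol 3.2, a man who needs a prohibited medication leaves the study.
- Under SAP 3.7.1, the Extension Phase ends at the last dose for men on open-label filgotinib. Standard of Care men who leave without entering the Monitoring Phase "will have the last date of standard of care estimated using the last of the following dates", and that list includes the last sperm collection.

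**The concern.** A proportion of men who ever meet a criterion rises with the number of times each man is examined, even if the risk at each examination is the same. If one sequence contributes more semen visits per man, its proportion is higher for that reason alone. If it contributes fewer, a higher risk per visit can be masked.

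The rules above could shorten follow-up on open-label filgotinib. Selection could lengthen it, because only Week 13 arthritis responders continue filgotinib. Readers will compare the columns, and the criteria matter: the decrease thresholds are what stop study drug and send a man to the Monitoring Phase. For adverse events of interest and serious adverse events over the whole study, the SAP does adjust for exposure (8.1.5.3 and 8.1.7). It specifies no such adjustment for these semen criteria.

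**Working it through.** **The plan's own figures.** The documents give no rate, precision or power for this display. The only sample-size figure is for Week 13: 200/(1 − 0.20) = 250, which reproduces exactly but does not bear on this point.

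**Visits possible.** From Week 39 to Week 156 every 13 weeks: (156 − 39)/13 + 1 = 10, in agreement with SAP Table 3-4.

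**Dependence on visits.** With risk q per visit and k independent visits, P(ever met) = 1 − (1 − q)^k. The documents give no long-term q and no visit counts, so q of 1% to 5% and the values of k are assumptions.

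| q per visit | 4 visits | 10 visits |
|---|---|---|
| 1% | 3.9% | 9.6% |
| 2% | 7.8% | 18.3% |
| 3% | 11.5% | 26.3% |
| 5% | 18.5% | 40.1% |

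- Equal k gives equal proportions at any q.
- A small gap matters little: at 3%, 8 visits give 21.6% and 9 visits give 1 − 0.97^9 = 24.0%.
- A large gap can reverse the order: 6% over 4 visits is 1 − 0.94^4 = 21.9%, below the 26.3% from 3% over 10 visits.

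**Gradual loss.** Let every man have the Week 39 visit, and let a fraction c leave per 13-week interval for reasons unrelated to semen. The share still at risk at visit j is [(1 − q)(1 − c)]^(j−1). Mean at-risk visits are the sum over j = 1 to 10, and P(ever met) is q times that sum. At q = 3%:

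- c = 0: mean 8.75 visits, 26.3% ever met, 26.3/8.75 = 3.0 per 100 visits.
- c = 15%: mean 4.87 visits, 14.6% ever met, 14.6/4.87 = 3.0 per 100 visits.

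Dividing by at-risk visits recovers the risk per visit.

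**Independence.** For q of 2% to 6%, independent visits give 18% (10 visits) against 11% (6 visits), up to 46% against 31%. With an assumed within-man correlation of 0.2 (beta-binomial), these become 10% against 8%, up to 28% against 22%. The dependence weakens but remains.

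**Overlap of criteria.** From the entry minima, the smallest falls that reach a confirmed abnormality are 1 − 5/15 = 66.7% (concentration), 1 − 20/40 = 50% (motility) and 1 − 10/30 = 66.7% (morphology). An eligible man with a confirmed abnormality therefore also meets a decrease threshold and leaves for the Monitoring Phase. One count of at-risk visits per sequence can serve all rows, apart from visits where a parameter is not evaluable.

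**The case against.** - **The pooled reading is an inference.** The SAP does not say ever met, and the definition of the at/after Week 39 set belongs in SAP 3.1.2, which is not in the copy read here. This stands as a caution. The missing by-visit wording, present in 6.5.2 and 6.6.3, still makes pooling the natural reading.
- **No comparison is planned.** Section 6.5 holds other displays. After Week 39 it specifies no difference, interval or test, and the listed semen endpoints are at Weeks 13 and 26, plus reversibility. This stands, and it limits the weight of the point.
- **Much is available elsewhere.** SAP 6.5.2 gives the concentration decrease by visit, and n by visit for motility and morphology. SAP 6.6.2 gives reversibility by parameter and sequence, SAP 4.2.1 summarizes time in the Extension Phase, and listings identify the men concerned. A reader might infer that 6.5.3 is the only long-term view of the threshold rule; it is not. A careful reader could approximate rates by hand, but the table itself would not show them.
- **Unequal visits are not shown.** All sequences share one schedule. Table 5-1 also removes Standard of Care men who need, for example, sulfasalazine, rituximab or more than 20 mg/day of prednisone. The Standard of Care end-date rule creates no semen visits. This stands: the documents show that follow-up could differ, not that it does.
- **A rate does not isolate the drug.** Continuing filgotinib is conditional on Week 13 response, so the sequences differ in more than treatment. This also stands.

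**Conclusion.** The point holds as a modest, inexpensive improvement to a descriptive table. On its natural reading, the at/after Week 39 part of SAP 6.5.3 mixes risk per visit with visits contributed. No by-visit proportion is planned for motility, morphology, the combined decrease or the confirmed abnormality.

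The size is unknown. The contrast of 11.5% with 26.3% rests on an assumed 3% per visit, independent visits, and 4 visits against 10. It shrinks with smaller gaps or within-man correlation, and is zero with equal visits.

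A reader might go further and infer that the table will hide a filgotinib excess, or create one. The documents do not support either: they give no visits per sequence, and the reasons for unequal follow-up act in both directions.

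**What to change.** In SAP 6.5.3, present every at/after Week 39 row by analysis visit with the number evaluable, as 6.5.2 does for the concentration decrease. In addition or instead, give first events per at-risk semen visit, or per 100 subject-years, with the exact Poisson 95% CI already defined in SAP 8.1.5.3, and show the number of at-risk visits per sequence. Keep the crude count. Where risk varies between men, the by-visit form is the safer of the two, because higher-risk men leave first and a single first-event rate then drifts with length of follow-up.

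Add a sentence stating that the sequences are not randomized groups, so the change removes the unequal-follow-up distortion only and does not isolate filgotinib's effect.

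The cost is SAP wording, or a documented change in the study report, and a slightly longer table. Intervals will be wide because events are likely to be few. No new data are needed.

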6.6. Exploratory Endpoints

6.6.1. Definition of the Exploratory Endpoints

The exploratory endpoints are:

- Percent of reversibility among subjects who experience a $\geq 50\%$ decrease in sperm concentration, and/or motility, and/or morphology
- Change from baseline in hormones, including LH, FSH, inhibin B, and total testosterone at Weeks 13 and 26

